Although these methods have provided insight into MVD, much remains unknown. For example, even the prevalence of MVD in patients with various types of cardiomyopathy is unclear, with different studies showing widely different rates. In part, this may be due to limitations of these imaging methods. For example, SPECT provides qualitative information regarding relative differences in regional blood flow, but is not able to assess global changes in myocardial blood flow. PET can quantify regional and global absolute blood flow, but these measurements may exhibit substantial variation in individual measurements depending upon the methodology that is employed (e.g. the arterial input function and/or the extraction model used).³ Both techniques can be affected by partial volume effects due to regional variation in LV wall thickness and the limited spatial resolution of imaging. Additionally, both PET and SPECT have difficulty distinguishing between reductions in blood flow due to ischemia versus scar tissue, which appears to be present in variable degrees depending on the type of cardiomyopathy. Thus, the influence of scar tissue on myocardial blood flow in patients with suspected MVD is unknown.

Cardiovascular magnetic resonance (CMR) is increasingly being used in clinical practice to evaluate cardiac disease. CMR employs a multifaceted imaging approach with separate techniques used to acquire separate sets of raw data, providing information on cardiac morphology, function, regional myocardial ischemia, scarring, and global myocardial perfusion reserve. The advantage of this approach is that image artifacts in one set of data will not affect the quality of the other datasets, and the datasets in combination can be used to distinguish separate pathophysiologies that could confound image interpretation. For example, perfusion defects could be due to ischemia or scar tissue, but since we will obtain both perfusion images and scar images, we will be able to resolve the etiology. Additionally, CMR provides high spatial resolution (over 10-fold higher than PET), and hence partial volume effects will be kept to a minimum and variability in measurements will be reduced.

In the proposed study, we will assess microvascular function as determined by a CMR measurement of whole-heart (global) perfusion reserve. Our laboratory has recently made optimizations to this technique (see below; **Figure 1**) which will improve the reproducibility of measurements. Our goal is

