The CMR methodology and analysis to be used are fully described in the references. The entire scan procedure and scan time should take around 45 minutes. A cardiologist or fellow will supervise the scan, assess/triage patients, and initiate treatment if needed. A schematic of the imaging procedure is shown in **Figure 3**.

1. Standard Scout images of the heart leading to double oblique horizontal long axis view (4-Chamber) of the heart
2. Cine Image of the horizontal long axis view of the heart
3. Prescribed double oblique short axis view of the heart with first slice at the insertion points of the mitral valve in diastole.
4. Cine images of the short axis of the left ventricle from the base to and including the apex for entire LV coverage.

[figure not shown]

Figure 3. Multifaceted CMR examination

5. Cine images of the long axis views of the heart (2 chamber, 3 chamber, 4 chamber).
6. MOLLI images will be obtained prior contrast administration.
7. Coronary sinus imaging at rest as described in Figure 1.
8. Patients and controls will receive either (a) regadenoson (0.4 mg IV) injection over 10 seconds followed by saline flush or (b) adenosine $140 \mu\text{g}\cdot\text{kg}^{-1}\cdot\text{min}^{-1}$ x 3 minutes. During the injection or infusion, the participants will be monitored (continuous ECG and blood pressure monitoring) for 3-4 minutes. Half of the participants will receive Regadenoson, while the remainder will receive adenosine. Any serious adverse reactions during or after vasodilator stress will be recorded.
9. Stress perfusion images of 4-5 short axis slices (basal, mid, and apical) per heart beat for 60 heart beats beginning after 1-1.5 minutes after the regadenoson injection.
10. Bolus contrast injection of 0.1 mmol/kg of gadolinium contrast (gadoteridol or gadoteric acid) followed at 30 cc of saline flush beginning beginning after 1-1.5 minutes after regadenoson administration or after 2 minutes of adenosine infusion.
11. Coronary sinus imaging during stress (Figure 1).
12. In those receiving regadenoson, aminophylline (100 mg IV) will be administered over 30-60 seconds after completion of coronary sinus imaging. If bronchospasm is noted, participants will be treated with inhaled albuterol metered dose inhaler.
13. After a 15 minutes wait period, rest perfusion images of 4-5 short axis slices per heart beat for 60 heart beats using the identical imaging location and parameters as the stress perfusion images.

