$$\text{Global Perfusion Reserve} = \frac{\text{coronary sinus blood flow during maximal vasodilation}}{\text{coronary sinus blood flow at rest}}$$

Coronary sinus blood flow will be measured by contouring the coronary sinus at each time point within the cardiac cycle on both the magnitude and phase CS-CMR images at each cardiac frame. Total coronary sinus blood flow is then calculated by summing the flow per cardiac frame over the cardiac cycle. A global perfusion reserve of <2.0 will be regarded as abnormal and consistent with MVD.

Flow measurements will undergo a baseline correction using basal myocardium reference region located closest to the coronary sinus during at late-systole or mid-diastole when the motion is the most static. The baseline correction was performed for each cardiac frame to get the corrected coronary sinus blood flow. Coronary sinus blood flow_{corr}=V_{corr}×A_{CS}, where coronary sinus blood flow_{corr} is baseline corrected. V_{corr} comes from subtracting mean velocity of static region of interest from CS velocities. A_{CS} is area of CS at each time frame.

For the secondary aims, specific analyses will also be performed for each CMR technique to determine myocardial scar size, extent of regional perfusion defects, and morphological and function characteristics such as LV mass, LVEF, and LV volume.

Myocardial scarring will be determined by visual inspection using the American Heart Association 17-segment model. A patient is adjudicated to have myocardial scarring if there is at least more than one quarter of a myocardial segment of DE. This is done to reduce the effect of imaging artifacts, which can occasionally mimic DE. The extent of regional scarring is scored according to the spatial extent of delayed hyperenhancement within each segment (0 = no hyperenhancement (HE); 1 = 1%–25% HE; 2 = 26%–50% HE; 3 = 51%–75% HE; and 4 = 76%–100% HE). Global infarct size will be calculated by contouring of hyperenhanced regions from the stack of short-axis of delayed enhancement CMR images.

Regional myocardial perfusion will be scored by visual inspection using the American Heart Association 17-segment model (minus the apex) for the presence or absence of perfusion abnormalities and the spatial extent of hypoperfusion within each segment. Perfusion defect size will be calculated by contouring of hypoenhanced regions from stress perfusion CMR images.

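### Perfusion defect size is contoured on stress images alone and no written analysis separates scar from ischaemia within it, so its correlation with MVD may partly reflect scar

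*Combined protocol and SAP*

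**What the plan says.** Scientific Rationale criticises PET and SPECT because they struggle to tell reduced flow due to ischaemia from reduced flow due to scar. It then says of CMR that "since we will obtain both perfusion images and scar images, we will be able to resolve the etiology".

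The synopsis (Secondary Endpoints) and Image Analysis list the metrics to be related to MVD as "myocardial scar size, extent of regional perfusion defects, and morphological and function characteristics". Secondary Objectives numbers the relation of MVD with scarring and the relation of MVD with regional perfusion defects as two separate items.

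Image Analysis defines the measures as follows:

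- **Perfusion, visual:** segments of the AHA model without the apex (16 segments) are scored "for the presence or absence of perfusion abnormalities and the spatial extent of hypoperfusion within each segment". The text does not say whether stress images, rest images or both are read.
- **Perfusion, contoured:** "Perfusion defect size will be calculated by contouring of hypoenhanced regions from stress perfusion CMR images".
- **Scar:** a 0 to 4 score per AHA segment, and in addition "Global infarct size will be calculated by contouring of hyperenhanced regions from the stack of short-axis of delayed enhancement CMR images".

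CMR Overview step 13 acquires rest perfusion "using the identical imaging location and parameters as the stress perfusion images". Step 15 acquires delayed enhancement. Statistical Methods contains only the sample size determination.

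**The concern.** Scientific Rationale accepts that a perfusion defect may be scar. A contour drawn on stress images alone cannot tell the two apart, and the images that could do so are acquired but given no stated role in the defect measure. If some scar lies inside the contour, the two secondary correlations (MVD with scar, MVD with perfusion defects) share a component, and a link between MVD and defects may be read as ischaemia when it partly reflects scar.

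This bears on the study's interpretive aim. In Pilot Data and Anticipated Findings, the hypertrophic example had both focal defects and scar, while the dilated example had no focal defects and minimal scar. The protocol suggests different sites of microvascular disease as one explanation. That reading is weaker if the defects in the first example are largely scar.

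**Working it through.** **1. Is the split written anywhere?** Setting the sections side by side:

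| Place | What it contributes | Rule that splits defect from scar? |
|---|---|---|
| Scientific Rationale | States that the cause of a defect will be resolved | Intention only |
| CMR Overview, steps 13 and 15 | Acquires rest perfusion and delayed enhancement | No |
| Image Analysis, perfusion | Segment score (image set not stated); contour on stress images | No |
| Image Analysis, scar | Segment score and contour on delayed enhancement | No |
| Synopsis and Secondary Objectives | Separate relations of MVD with scar and with defects | No adjustment for scar |
| Statistical Methods | Sample size for MVD prevalence | No |

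There is no scar subtraction, stress-versus-rest comparison, segment match or scar-adjusted correlation.

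**2. Which slices match?** Rest perfusion matches stress perfusion (step 13). Delayed-enhancement slices are tied to the cine locations (step 15b, and item 7 of CMR details and parameters), not to the 4-5 perfusion slices. Perfusion and scar do share the AHA segment model.

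**3. How large could the overlap be?** The plan gives no figure to reproduce, and no standard deviations, correlations or share of scar that appears dark at stress. What follows is an illustration on assumed inputs. Extent of MVD is taken to be the global perfusion reserve, G.

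Let stress defect D = I + f·S, where I is ischaemic defect, S is scar and f is the share of scar inside the stress contour. Let k = SD(S)/SD(I). Assume that I and S are independent, corr(I, G) = 0 and corr(S, G) = -0.50. Then

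corr(D, S) = f·k / √(1 + (f·k)²)

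corr(D, G) = -0.50 × corr(D, S)

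| f | k | corr(D, S) | corr(D, G) |
|---|---|---|---|
| 0 | any | 0 | 0 |
| 0.5 | 0.5 | 0.24 | -0.12 |
| 0.5 | 1 | 0.45 | -0.22 |
| 0.5 | 2 | 0.71 | -0.35 |
| 1 | 0.5 | 0.45 | -0.22 |
| 1 | 1 | 0.71 | -0.35 |
| 1 | 2 | 0.89 | -0.45 |

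For f = 1 and k = 1: -0.50/√2 = -0.354. With n = 30 (one cardiomyopathy group), the two-sided 5% critical value is 2.048/√(28 + 2.048²) = 0.361, so the expected value falls just short of it. By the Fisher z approximation, atanh(0.354) = 0.370 and 0.370 × √27 = 1.92, so the chance of a significant result is Φ(1.92 - 1.96), about 0.48. If both groups were pooled (n = 60), 0.370 × √57 = 2.79 and the chance is Φ(0.83), about 0.80. Ischaemic defect has no relation to G in this scenario.

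**4. Would adjustment remove it?** In the same scenario the numerator of the partial correlation of D with G given S is -0.354 - (0.707)(-0.50) = 0. Adjusting for scar removes the artefact.

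**The case against.** The other side has several good arguments.

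- **The defect is never called ischaemic.** The plan speaks of perfusion defects throughout and measures scar separately. A reader might infer that scar is being counted as ischaemia, but the documents do not say so. The contour is a total stress defect, which is a legitimate quantity. This stands.
- **The method may lie in the references.** CMR Overview says "The CMR methodology and analysis to be used are fully described in the references", and the section describing the centre cites references 11 and 12 for combining stress perfusion with delayed enhancement to tell ischaemia from scar. A reader might infer that the separation will not be made. The documents support only that it is not written out. Still, a general pointer does not override the specific stress-only contour in Image Analysis. By their titles, those two references concern detection of coronary artery disease, which Patient Selection excludes.
- **The visual score is not limited to stress images,** and scar is scored on the same segment model. The endpoint could rest on that score. This stands, but nothing says which perfusion measure is used or that the two scores are to be crossed.
- **Containment is unproven.** A reader might infer that the defect measure contains the scar measure. No document says that all scar is dark at stress, and the two are contoured on different slice sets. The correlation between them runs from 0 to 0.89 over the assumptions above.
- **The illustration is only a scenario.** This also stands: -0.35 is below the 0.36 threshold at n = 30, and other inputs give less or more.

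**Conclusion.** The point holds as a gap in specification with a real consequence. The contoured measure uses stress images alone, and no written analysis delivers the separation that Scientific Rationale promises. The MVD-defect correlation is therefore open to being partly driven by scar.

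The size is unknown. With an assumed correlation of -0.50 between scar and perfusion reserve, and none for ischaemic defect, the induced correlation runs from 0 (no scar in the contour) to -0.45 (all scar in the contour, scar SD twice the ischaemic SD), and is -0.35 with equal variances and all scar dark at stress. All of these figures assume that scar and ischaemic defect are independent.

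Only the secondary endpoint is touched. The primary endpoint is a coronary sinus flow ratio below 2.0, and neither it nor the sample size uses the perfusion contour. The change is worth making because it is cheap and serves a stated aim, but it does not threaten the main result.

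**What to change.** In Image Analysis:

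1. State which images (stress, rest or both) the visual perfusion score reads.
2. Classify each of the 16 AHA segments with a stress defect as with or without matching delayed enhancement, and with or without a matching rest defect. Fix in advance which delayed-enhancement score counts as a match.
3. Keep the stress contour as total stress defect size, and add a scar-free defect extent from the segments without a match.

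In Statistical Methods, report the MVD correlation for total and for scar-free defect. Adjusting the MVD-defect correlation for scar size is an alternative or an addition.

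Pixel-area subtraction should not be required. Delayed-enhancement slices follow the cine locations, so subtraction would need an image registration that the plan does not describe.

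The cost is a little extra analysis of readings already planned, with no new scan or reader. Segment-level classification is coarser: a segment with a small scar inside a larger ischaemic defect is classed as matched, so scar-free extent may be understated. Reporting both versions makes this visible.
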